2.1. Scheme

Patients will be randomized 1:1 to receive treatment daily for 4 consecutive weeks versus sham, followed by an open-label phase for additional 4 consecutive weeks.

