2.2. Primary Objective

The primary objective is to determine the difference in the Numerical Pain Scale score between the baseline screening call and at week 4 in the treatment group compared with the same difference in the placebo or sham group.

The Numerical Pain Scale is an 11-point scale (0-10) that includes guides to assist in the

determination of the pain level.

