3.1. Primary

- QUELL FLEX therapy reduces pain scores in NMO patients on the Numerical Pain Scale at the week 4 study visit compared to baseline/screening visit, and this reduction is significantly greater compared to the reduction due to sham treatment during the same time period. Power for this study is calculated based on our previous study using a TENS unit (Scrambler) in the same patient population.

[figure not shown]

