3.2. Secondary

- QUELL FLEX therapy is an acceptable treatment measured by compliance and patient survey.
- Patients who were randomized initially to the sham arm will show a reduction in pain score after crossing over into the open label arm. In contrast, the patients in the treatment arm will not necessarily show additional benefit after rolling over in the open label arm.
- The “average” and “worst” pain scores will decline in the treatment arm and not necessarily in the sham arm.
- As pain is a primary driver of quality of life, quality of life will improve with treatment compared to sham.
- Patients for whom QUELL FLEX works well may choose to reduce their intake of pain medications.

4. Background and Rationale

4.1. Etiology and current treatment of central neuropathic pain in patients with neuromyelitis optica spectrum disorder

Neuromyelitis optica spectrum disorder (NMOSD) is an autoimmune disease of the central nervous system (CNS) that preferentially causes recurrent inflammatory attacks in the optic nerves and spinal cord, leading to blindness, paralysis and death. Despite these devastating consequences of the disease, patients have reported that pain is among the most prevalent and debilitating symptoms.

In particular, central neuropathic pain (CNP) is pervasive, severe, intractable to treatment, and affects 62-91% of patients with NMOSD. CNP is described as agonizing burning, stabbing, shooting, tingling or squeezing

Figure 1. Cross-section of the spinal cord depicting spinal tracts.

From:

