4.2.3. Data on Quell Relief

In a study for Quell TENS on back pain, the following results were reported:

“After six weeks, those in the Experimental group reported lower “worst” pain scores and less overall interference than those in the Control group ($p<0.025$). After three months those assigned to the Experimental group (hfTENS device) reported significantly less pain (worst, least, average, now) than those in the Control condition ($p<0.01$; Table 3). Pre-post comparisons on average pain intensity on the BPI showed significant groups differences (Experimental=1.24; Control=-0.03; $t=2.74$; $p<0.01$) with 31.0% of the Experimental group showing ≥ 2.0 differences vs. 12.9% among the Control group. Those in the Experimental group also reported less overall pain-related interference (general activity, mood, walking ability, work, relation with others, sleep, and enjoyment of life) compared with the Control group ($p<0.025$). Also, subjects assigned to use the hfTENS reported reduced pain catastrophizing scores compared with the Controls ($p<0.025$). No differences were noted between groups on the self-report questionnaires assessing disability (PDI) and anxiety and depression (HADS). Both groups demonstrated a reduction in the use of prescription pain medication, but no differences were found between groups.”

TENS for Neuropathic Pain in NMOSD

Principal Investigator: [name], PhD

5. Patient Population

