11.2. Efficacy

Change in pain score will be calculated by subtracting the patient's week 4 score from his or her baseline value prior to treatment initiation. Change in scores will be summarized using means and standard deviations provided the resulting distribution is symmetric, otherwise medians and interquartile ranges will be used. Provided the resulting distribution of pain scores is roughly normal, we will use a two-sample t-test to compare the QUELL FLEX and sham groups. Previous studies suggest that the average pain value at baseline is at least 4 on the 0-10 numerical rating scale with a standard deviation of the original pain value expected to fall in the range of 1-1.5 in this patient population. As such, a conservative estimate of the standard deviation would be approximately 20%. With 19 patients in each arm and under these assumptions, we will have the ability to detect a change of 2.0 points in the QUELL FLEX group with power of 0.90. If the change score distribution is highly skewed, Wilcoxon's signed rank test will be utilized instead.

To account for ~20% dropout rate, we will add 4 subjects to each arm for a total of 23 subjects per arm. We included a dropout rate of ~20% based on previous studies with this device. We will run a sensitivity analysis to determine if the drop-out rate in either arm had an impact on the trial results.

A 20% reduction in pain has been previously determined to be a clinically meaningful improvement, we will report the number and percent of patients from each group who achieve this benchmark.

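### The skewed-data fallback for the primary endpoint names Wilcoxon's signed-rank test, which cannot compare two independent arms; a rank-sum test is needed

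*Combined protocol and SAP*

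**What the plan says.** The primary question is between arms. Section 2.2 takes the change in Numerical Pain Scale score from the baseline screening call to week 4 "in the treatment group compared with the same difference in the placebo or sham group". Section 3.1 adds that "this reduction is significantly greater compared to the reduction due to sham treatment during the same time period". The arms are independent: under 2.1, "Patients will be randomized 1:1 to receive treatment daily for 4 consecutive weeks versus sham", and 6.4 describes blocks of four with two assignments to each arm, without matching any patient to another.

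Section 11.2 defines one change score per patient, baseline minus week 4. If the distribution is roughly normal, "we will use a two-sample t-test to compare the QUELL FLEX and sham groups". The power statement follows: with 19 per arm, "we will have the ability to detect a change of 2.0 points in the QUELL FLEX group with power of 0.90". Then comes the fallback: "If the change score distribution is highly skewed, Wilcoxon's signed rank test will be utilized instead". No section names a two-sample rank test, and no threshold is given for the skewness that triggers the switch.

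**The concern.** The fallback takes the place of the two-sample t-test, so in the skewed case it is the only test named for the primary endpoint. The signed-rank test asks whether a single set of changes, or of paired differences, is centred on zero. With one change score per patient in two unpaired arms, it has nowhere to enter the sham group as a comparator.

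An analyst who reaches this branch has two options. One is to run the named test within the QUELL FLEX arm, where improvement that sham patients share can be reported as a device effect. The other is to substitute rank-sum, which answers the right question but departs from the written plan, possibly after the data have been seen. The power sentence speaks of a change in the QUELL FLEX group, not a difference from sham, which leaves the within-arm reading open.

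**Working it through.** **What each test uses.** Let dᵢ be baseline minus week 4 for patient i.

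- Signed-rank, one arm of n = 19: rank the |dᵢ| and let W⁺ be the sum of ranks with dᵢ > 0. With no zeros or ties, its null mean is n(n+1)/4 = 19·20/4 = 95 and its variance is n(n+1)(2n+1)/24 = 19·20·39/24 = 617.5. If all 19 QUELL FLEX patients improve, W⁺ = 19·20/2 = 190 and z = (190 − 95)/√617.5 = 3.82. Sham data do not enter, so z is the same even if every sham patient improves equally.
- Rank-sum, 19 + 19: rank all 38 changes together and sum the QUELL FLEX ranks. The null mean is 19·39/2 = 370.5. Improvement shared by both arms leaves this statistic centred on its null value.

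**The stated power.** The protocol gives no alpha, sidedness or SD of the change score, so 0.90 at 19 per arm cannot be reproduced uniquely. Reading the approximate 20% SD as 2.0 points (an assumption), the two-sample noncentrality is 2.0/(2.0·√(2/19)) = 3.08. The normal approximation then gives Φ(3.08 − 1.96) = 0.87 two-sided and Φ(3.08 − 1.645) = 0.92 one-sided; the t calculation gives 0.85 and 0.92. The figure is consistent with a between-arm calculation under some standard choices. The present point does not depend on it.

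**Size of the consequence if signed-rank is run in the QUELL FLEX arm.** Assumptions: both arms have the same distribution (true difference zero); 19 per arm; shifted-exponential changes rounded to whole points; two-sided 5%; 20,000 simulated trials per scenario. Rejection rates:

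| Shared mean improvement (points) | 0 | 0.5 | 1 | 1.5 |
|---|---|---|---|---|
| Signed-rank, SD 2, skew toward improvement | 10% | 11% | 54% | >99% |
| Signed-rank, SD 2, skew toward worsening | 10% | 33% | 64% | 84% |
| Signed-rank, SD 1.5 to 2.5, both skews | 8–10% | 6–43% | 34–>99% | 74–>99% |
| Rank-sum between arms, all scenarios | ~5% | ~5% | ~5% | ~5% |

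Three qualifications apply.

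- These are two-sided rejections. At zero mean change with skew toward improvement, almost all of the 10% points to worsening (0.5% to benefit). With the opposite skew the rejections point mostly to benefit, because the median then lies above a zero mean.
- The >99% entries are partly an artefact of the shape. A shifted exponential skewed toward improvement has a floor at mean minus SD. For SD 2 at 1.5 points, and for SD 1.5 at 1 point, the floor is −0.5, so after rounding no patient worsens. A milder gamma shape (skewness 1) gives 31–83% at 1 point, in place of 34–>99%.
- Keeping only trials with sample skewness above 1 in absolute value (an assumed trigger; SD 2, skew toward improvement) gives 11%, 10%, 52% and >99%.

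**The other literal reading.** Pairing patients arbitrarily across arms and applying signed-rank to the differences rejects in 4–6% of trials. That does not inflate false positives, but the protocol defines no partners, and a dropout leaves a partner unmatched.

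**The case against.** The strongest reply is that the intent is recoverable. The fallback stands in for a test that explicitly compares the two groups, and 2.2 and 3.1 both state a between-arm question. A competent analyst would read rank-sum, and the practical result would be an undocumented correction, not a false claim of benefit. The sample size also fits a between-arm reading better. At SD 2.0, a one-sample t-test of a 2.0-point change needs about 13 patients for 90% power at two-sided 5%; a one-sample calculation gives 0.90 at 19 only with an SD of about 2.5 (t) to 2.7 (normal approximation).

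The false-positive scenario also needs three things together: the fallback is triggered, the test is run within one arm, and sham patients improve materially. The protocol does not lead one to expect the last. Section 3.2 says average and worst "pain scores will decline in the treatment arm and not necessarily in the sham arm", and the only control-arm change quoted, in 4.2.3, is −0.03, from a back-pain study whose control is not described as sham.

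All of this stands as a limit on the consequence, and the rates above should be read as illustration. It does not rescue the wording. The sentence governs the primary endpoint, names a test that cannot do the job, and is corrected nowhere. A primary test should not depend on the analyst guessing what was meant.

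**Conclusion.** The concern holds. The named fallback is the wrong test for the primary comparison; this follows from the text alone and needs no assumption. It should be corrected before analysis.

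The numerical consequence is conditional. If signed-rank were run within the QUELL FLEX arm and both arms improved by 1 point, it would reject in roughly a third to four-fifths of trials under the milder skewed shape with SD 1.5 to 2.5, against about 5% for rank-sum. At 0.5 point the exponential scenarios give 6–43%. The assumptions are 19 per arm, identical arms and a two-sided 5% level. The chance that the fallback is triggered cannot be estimated from the protocol, so none of these rates is the trial's overall type I error.

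**What to change.** In 11.2, replace the signed-rank test by: *Wilcoxon rank-sum (Mann-Whitney) test comparing the change scores of the QUELL FLEX and sham arms*. That is the only necessary change. It costs one phrase and needs no new data or patients. In a check with 600 simulated trials per setting, rank-sum at 19 per arm and SD 2.0 had power of about 0.85 (normal changes) and 0.95 (skewed changes) for a true 2.0-point difference.

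Two additions are optional: define what counts as highly skewed, or fix one between-arm test as primary with the other as a sensitivity analysis; and report a Hodges-Lehmann estimate of the between-arm shift alongside the rank test.

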2.3. Secondary

Six secondary objectives are intended to collect additional information about the potential benefit of QUELL FLEX:

- A. The difference in pain scores at the end of the open label phase compared to the end of the initial blinded phase.
- B. A change in the “worst” pain score in the treatment arm vs. the sham arm between the baseline screening call and week 4; and the change in the “worst” pain from baseline to week 8 for all subjects.
- C. A change in the “average” pain score in the treatment arm vs. the sham arm between the baseline screening call and week 4; and the change in the “average” pain from baseline to week 8 for all subjects.
- D. The number of patients who withdraw because of poor compliance. We expect a higher withdrawal and non-compliance rate in the sham group.
- E. Quality of life surveys will be conducted before and after the treatment phase and at the end of the study to determine if the QUELL FLEX treatment impacts overall quality of life.
- F. Reduction in pain medication use over the course of the study.

TENS for Neuropathic Pain in NMOSD

Principal Investigator: [name], PhD

3. Hypotheses

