6.2. Recruitment

We plan to recruit 46 consecutive patients with NMOSD (23 per arm) with a diagnosis of NMOSD based on the 2015 international consensus diagnostic criteria and the presence of neuropathic pain. Trial information will be made available through clinicaltrials.gov.

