6.4 Randomization and Blinding

Randomization would be done in blocks of 4 (e.g. 2 placebo and 2 treatment assignments) assigned at random at the beginning of the study for each 4 patients enrolled in the study consecutively. This ensures that it is not possible to predict the arm assignment of patients as we unblind them in groups of 4 at the conclusion of each patient's participation in the study.

Blinding keys, including the arm assignment of the patient, will be sealed in envelopes and not opened until unblinding occurs for the 4-patient-block.

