10. At the conclusion of the 4-week experimental arm, all patients will be shipped a new QUELL FLEX device for use in the 4-week open label phase. This one will be functional. The experimental QUELL FLEX devices will be returned in the same shipping box to the study team. Study staff will administer the SF-36 Quality of Life questionnaire.
11. In the 4-week open label phase, patients will continue to use the device with the electrodes in the same position. Weekly pain scores will be documented as before as well as the SF-36 Quality of Life questionnaire at the conclusion of the 4-week open label period.
12. At the conclusion of the 4-week open label period for the 4-patient block, blinding will be unsealed and reported to the patients. They will then have the opportunity to keep the functional QUELL FLEX if they wish.
13. Four and eight weeks after the completion of the open label phase, patients will be called for a wellness check and asked to rate their pain again.
14. Adverse Events will be monitored and documented weekly.

6.5.1.2. Treatment follow-up:

Patients will be contacted by Zoom weekly during the experimental and open-label phases to check in on them, and will be asked weekly to report their pain score. At the conclusion of the experimental phase and at the end of the study, patients will be asked again to complete the Short Form-36 Health Inventory (SF-36).

[figure not shown]
TENS for Neuropathic Pain in NMOSD

Principal Investigator: [name], PhD

Patient-Reported Outcomes

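### Adding 4 patients to 19 per arm covers a dropout of about 17%, not 20%; at 20% about 18 per arm remain, at a cost of roughly one power point

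*Combined protocol and SAP*

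**What the plan says.** Section 11.2 (Efficacy) gives the power statement: "With 19 patients in each arm and under these assumptions, we will have the ability to detect a change of 2.0 points". The power it attaches to this is 0.90. The comparison is a two-sample t-test on the change in pain score from baseline to week 4. The same section then inflates the size: "To account for ~20% dropout rate, we will add 4 subjects to each arm for a total of 23 subjects per arm". It attributes the rate of about 20% to earlier studies with the device and promises a sensitivity analysis of dropout in either arm.

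Section 6.2 carries the result forward: "We plan to recruit 46 consecutive patients with NMOSD (23 per arm". Section 5.3 gives the same total of 46.

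Section 11.2 states neither alpha nor sidedness. It expects an SD of 1 to 1.5 for the baseline score, then gives a conservative SD of about 20% without saying 20% of what.

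On allocation, section 6.4 says "Randomization would be done in blocks of 4 (e.g. 2 placebo and 2 treatment assignments", and step 12 of section 6.5.1.1 says "At the conclusion of the 4-week open label period for the 4-patient block, blinding will be unsealed".

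**The concern.** The allowance is calculated as a percentage of the patients who must remain, but dropout is a percentage of those who enter. Four is 21% of 19 but only 17% of 23. At the plan's own planning rate, the evaluable number that carries the power statement is therefore not expected to be reached. Readers will take 23 per arm as the size that protects 0.90 power against a 20% loss, and the figures do not show that.

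A smaller matter is that 46 is not a multiple of the block size of 4. The 23:23 split is therefore a target rather than something the described randomisation guarantees, and the unsealing rule, written for a 4-patient block, does not mention an unfinished one.

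**Working it through.** **Inputs.** From section 11.2: 19 evaluable per arm, a difference of 2.0 points, power 0.90, dropout about 20%, 4 added per arm, 23 enrolled per arm. From section 6.2: 46 in total. From section 6.4: blocks of 4, two per arm. Assumed, because the plan does not give them: alpha 0.05, two-sided unless noted, and the SD as shown below.

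**Step 1: reproduce the plan's figure.** n × (1 + d) = 19 × 1.20 = 22.8, rounded up to 23. This matches the stated 23 per arm.

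**Step 2: inflate on the enrolled number.** n / (1 − d) = 19 / 0.80 = 23.75, rounded up to 24 per arm, 48 in total. Check: 24 × 0.80 = 19.2.

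**Step 3: what 23 per arm covers.** The largest loss that leaves 19 is 4 / 23 = 17.4%. Because the plan gives the rate only approximately, the expected number remaining, 23 × (1 − d), is shown over a range:

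| Dropout | Remaining of 23 |
|---|---|
| 15% | 19.55 |
| 17% | 19.09 |
| 18% | 18.86 |
| 20% | 18.40 |
| 22% | 17.94 |
| 25% | 17.25 |

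**Step 4: effect on power.** Power of the two-sample t-test (noncentral t) for a 2.0-point difference, by evaluable number per arm. The SD of 1.85 is back-solved so that 19 per arm gives 0.90; it does not stand in the plan.

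| SD and alpha | 19 | 18.4 | 18 |
|---|---|---|---|
| 1.85, two-sided 0.05 (back-solved) | 0.900 | 0.890 | 0.883 |
| 1.5 (top of the stated baseline range), two-sided 0.05 | 0.979 | 0.976 | 0.973 |
| 2.0 (20% of the 10-point scale), two-sided 0.05 | 0.851 | 0.839 | 0.830 |
| 2.0, one-sided 0.05 | 0.916 | 0.908 | 0.902 |

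Within each row, going from 19 to 18.4 costs at most about 1.2 points and going to 18 at most about 2. The rows differ from one another by far more than that.

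**Step 5: the last block.** 46 / 4 = 11.5, so 11 full blocks give 22:22 and two patients enter an unfinished 2:2 block. They fall in the same arm with probability 2/6 = 1/3, giving 24:22; otherwise the split is 23:23. At SD 1.85 and 20% loss, power is 0.8895 for 24:22 and 0.8901 for 23:23.

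**The case against.** **The rate is approximate.** The plan writes its dropout rate with a tilde, and 17.4% can fairly be read as about 20%. The gap is 0.6 of a patient per arm. This stands as a limit on the size of the point. It does not remove it: an approximate 20% could as well be 22%, and the allowance has no margin above 17.4%.

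**The power loss rests on an assumed SD and alpha.** This stands. With an SD of 1.5, or with an SD of 2.0 and a one-sided test, power stays above 0.90 even at 18 per arm. With an SD of 2.0 and a two-sided test it is below 0.90 before any dropout. A reader might infer from the shortfall that the trial is underpowered; the documents do not support that.

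**The chance of keeping 19 may look alarming.** With independent 20% dropout, at least 19 of 23 remain with probability 0.50 per arm and 0.25 in both arms. But a correctly inflated 24 gives only 0.66 and 0.43. Dropout inflation aims at the expected number and does not guarantee it, so these probabilities are not evidence of a serious defect.

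**The sham arm might be thought to fall further short.** Objective D in section 2.3 says "We expect a higher withdrawal and non-compliance rate in the sham group". That gives no rate and concerns withdrawal for poor compliance. Section 6.8.1 treats non-compliance as a reason to stop the intervention, section 6.8.2 does not list it among reasons for leaving the study, and section 6.8 continues follow-up unless the patient refuses. A non-compliant patient can still give a week 4 score. If 20% is the overall rate, more loss on sham also means less on active: at 15% and 25%, power at SD 1.85 is 0.889 against 0.890.

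**The unfinished block might be thought to need repair.** Its worst result, 24:22, has a negligible effect. Adding a block of 2 would be a poor remedy, since knowing one assignment in it reveals the other.

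**Conclusion.** The point holds as a minor arithmetic correction. The inflation in section 11.2 multiplies where it should divide, so 23 per arm protects 19 evaluable patients only up to a loss of about 17%; at 20% about 18.4 are expected. This part needs no assumption beyond the plan's own figures.

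The cost is about one power point, from 0.90 to 0.89 at 18.4 per arm and 0.88 at 18. Those figures depend on an assumed two-sided alpha of 0.05 and a back-solved SD of about 1.85. The missing alpha and sidedness, and the SD without a base, matter more to the power statement than the missing patient per arm.

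The incomplete last block is at most a wording note.

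**What to change.** In section 11.2, replace the dropout sentence with a statement that 23 enrolled per arm keep 19 evaluable per arm for dropout up to about 17%, and that about 18 per arm remain at 20%. Give the power at 18 per arm, and state the SD of the change score (in points), alpha and sidedness used. The power at 18 cannot be calculated from the plan until those three are fixed.

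This costs a few lines of text and no patients; the power quoted at 20% dropout may be slightly less favourable than 0.90, depending on the SD and alpha chosen.

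Enrolling 24 per arm would be an alternative: 48 in total is 12 full blocks of 4, and 19.2 per arm are expected after a 20% loss. It costs two more patients and is not required.

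If 46 is kept, one sentence in section 6.4 or in step 12 of section 6.5.1.1 could say when a last, unfinished block is unsealed. The block structure need not change.
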